10.3.2.3 Main analysis

The primary statistical analysis will be performed on the mFAS.

The absolute change in WASO will be analyzed using the MCP-Mod approach [Bretz 2005, Pinheiro 2006] using a set of multiple contrast tests (MCTs) to establish the existence of a dose response that is based on a pre-specified set of dose-response models describing the potential dose-response relationship.

[figure not shown]
The following pre-defined dose-response models are considered: one linear, and three E_{\max} models. Figure 2 shows the candidate dose-response curves for the mean reduction from baseline in WASO.

The analysis will be performed using the R-package *DoseFinding* [Bornkamp 2016]. For each candidate model, a t-statistic is derived based on a linear combination of the mean response estimates per individual dose and using optimal contrast coefficients corresponding to the candidate model. The mean response estimates are the least-squares mean (for change from baseline in WASO) of each dose group estimated by fitting a mixed model adjusted for baseline WASO, with dose group and period as fixed effects, and subject as a random effect. A dose-response relationship is demonstrated if at least one of the four MCTs has an adjusted p-value < 0.05. The best-fitting model based on

Akaike's Information Criterion will be used to estimate the target dose, defined as the dose that achieves a placebo-corrected mean reduction from baseline in WASO of at least 15 minutes with a 95% confidence interval excluding 0.

The primary endpoint will also be summarized by dose using the mean, median, standard deviation, standard error, quartiles, minimum, maximum and 95% confidence limits of the mean.

Figure 2 Candidate dose-response curves

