10.5 Sample size

The following sample-size calculations are based on MCP-Mod methodology [Pinheiro 2006]. Computations were performed in R version 3.1.2 using the *DoseFinding* package.

Assuming the maximum mean reduction in WASO from baseline to Days 1 and 2 with an ACT-541468 dose is 25 minutes (standard deviation = 40 minutes) larger than with placebo, and values from 8% of subjects are not available for analysis, a total sample size of approximately 50 (i.e., 10 subjects per sequence allocated in a 1:1:1:1:1 ratio) provides between 89–92% power (power is 90% when averaged over all candidate models [Figure 2]) to reject the null hypothesis of no dose response at a 5% two-sided significance level, while the alternative hypothesis is that a dose-response relationship exists.

The between-subject standard deviation in WASO across all arms is expected to be no more than 40 minutes. The sample size is conservative, since a correlation of zero (and non-negative) is assumed between assessments across dose within the same subject.

Assuming the maximum mean reduction in WASO is considered to be 20 minutes larger than with placebo, a sample size of 71 subjects (with no dropout) are required. This number decreases to 32 subjects if we consider a maximum reduction of 30 minutes compared to placebo.

This study is powered to detect a dose-response signal given the pre-defined set of candidate dose-response curves shown in [Figure 2](#). The study is not specifically powered to show the superiority of individual doses of ACT-541468 compared to placebo nor to provide a certain precision in estimation of a given target dose.

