#### 7.3.2.1 Implementation of the MCP step

The MCP step consists of testing a set of optimal contrasts: each testing contrast representing one of the pre-specified dose response models. This step addresses the issue of possible model misspecifications (the reason why multiple candidate dose response shapes are pre-defined) and also includes the associated adjustments for multiplicity within a rigorous hypothesis testing framework.

For a single given candidate dose response model, the optimal contrast for testing the hypothesis of a flat dose-response profile with maximal power is given by:

$$\mathbf{c}_m^{\text{opt}} \propto \hat{\mathbf{S}}^{-1} \left( \boldsymbol{\mu}_m^0 - \frac{\boldsymbol{\mu}_m^{0'} \hat{\mathbf{S}}^{-1} \mathbf{1}}{\mathbf{1}' \hat{\mathbf{S}}^{-1} \mathbf{1}} \right)$$

Where  $\boldsymbol{\mu}_m^0$  is the standardized mean response at each dose for a given candidate dose response model (m) and  $\hat{\mathbf{S}}$  denotes the estimated variance-covariance of  $\hat{\boldsymbol{\mu}}_d$  [Pinheiro 2014] (i.e., the estimated mean response per individual dose level from the observed data; further details below).

In the calculation of the optimal contrasts (one for each candidate dose response model  $\mathbf{c}_1^{\text{opt}}, \dots, \mathbf{c}_4^{\text{opt}}$ ),  $\boldsymbol{\mu}_m^0$  relies on the standardized form of the dose response model (not the complete functional form).

For convenience, the contrast coefficients are normalized such that  $\|\mathbf{c}^{\text{opt}}\| = 1$ .

Once data are available, the optimal contrasts are applied to  $\hat{\boldsymbol{\mu}}_d$ .

For each candidate dose response model (m), the null hypothesis  $H_0: (\mathbf{c}_m^{\text{opt}})' \boldsymbol{\mu} = 0$  (absence of a dose-response relationship) will be tested against the two-sided alternative  $H_1: (\mathbf{c}_m^{\text{opt}})' \boldsymbol{\mu} \neq 0$  (existence of a dose response).  $\boldsymbol{\mu}$  is the true, but unknown vector of means.

The t-test statistic associated with each of the candidate dose response models is given by

$$T_m = \frac{(\mathbf{c}_m^{\text{opt}})' \hat{\boldsymbol{\mu}}}{\left[ \mathbf{C}' \hat{\mathbf{S}} \mathbf{C} \right]_{m,m}^{1/2}}$$

with  $[A]_{m,m}$  denoting the  $m^{\text{th}}$  diagonal element of the matrix A, and  $\mathbf{C} = [\mathbf{c}_1^{\text{opt}}, \dots, \mathbf{c}_4^{\text{opt}}]$  representing the matrix containing the optimal contrasts.

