The test statistic used for establishing an overall dose-response signal will be the maximum of the individual model contrast test statistics  $T_{\max} = \max_m(T_m)$ , or alternatively, the associated multiplicity adjusted  $p$ -value associated with  $T_{\max}$ .

Analysis will only proceed to the modeling (Mod) step if a statistically significant dose-response signal is established, i.e., the null hypothesis is rejected under any candidate dose response model (adjusted two-sided  $p$ -value < 0.05).

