#### *First stage*

A linear mixed effects model (first stage model) will be used to calculate estimates for  $\hat{\mu}_d$  (i.e., least squares [LS] mean estimates for each ACT-541468 dose level and placebo) and  $\hat{S}$  (i.e., variance-covariance matrix of  $\hat{\mu}_d$ ).

The change from baseline in WASO (assumed to be normally distributed) will be modeled using a fixed effect for dose group (placebo and each ACT-541468 dose level), an additional fixed effect for period (five periods), a linear slope to adjust for WASO at baseline, and a random effect for subject.

The variance of the change from baseline in WASO is assumed to be constant across each dose group, therefore a compound symmetry structure for  $\hat{S}$  will be considered.

The LS mean for each treatment group will be displayed along with associated standard errors and 95% confidence intervals (CIs). For each ACT-541468 dose level comparison to placebo, the placebo-adjusted LS mean will be displayed along with associated standard error, 95% CI and unadjusted two-sided  $p$ -value.

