### **13.5 Absolute change from baseline**

The absolute change from baseline is defined as post-baseline value minus baseline value. A positive number indicates an increase as compared to baseline.

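### SAP 7.3.2.1 leaves the absolute value out of the two-sided primary test statistic, so the formula contradicts the decision rule that follows it

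*SAP*

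**What the plan says.** SAP 7.3.2.1 builds one optimal contrast for each of four candidate models. Each null hypothesis "will be tested against the two-sided alternative". The section then names the overall statistic: "The test statistic used for establishing an overall dose-response signal will be the maximum of the individual model contrast test statistics", written T_max = max_m(T_m), or equivalently its adjusted p-value. The sentence after that lets the analysis go on to modelling if "the null hypothesis is rejected under any candidate dose response model", with an adjusted two-sided p-value below 0.05.

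Protocol 10.3.2.3 has the same decision rule: "A dose-response relationship is demonstrated if at least one of the four MCTs has an adjusted p-value < 0.05". Protocol 10.5 powers the study "to reject the null hypothesis of no dose response at a 5% two-sided significance level".

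Three further statements fix the sign:

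- SAP 13.5: "The absolute change from baseline is defined as post-baseline value minus baseline value", and "A positive number indicates an increase as compared to baseline".
- SAP 7.3.2.2, first stage: "The change from baseline in WASO (assumed to be normally distributed) will be modeled using a fixed effect for dose group". The response is therefore the change, not the reduction.
- SAP 7.3.1.1 and 7.3.2.1: the contrasts use only the standardized shapes, d/(ED50 + d) or d, which increase with dose.

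SAP 7.3.2.3 points the other way. For the target dose it requires the lower confidence limit of the predicted mean to lie above the observed placebo mean, which makes sense only if higher values are better.

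**The concern.** WASO falls when the drug works. On the post-minus-baseline scale the dose means then decrease with dose, while the contrast coefficients increase from placebo to 50 mg. Every T_m is negative under benefit, and the maximum of four negative numbers is the one nearest zero.

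The formula can then be applied in two ways, and both go wrong. Taking a two-sided p-value for max(T_m) tests the least favourable contrast, so in effect all four must be significant instead of any one. Using the upper tail of max(T_m) detects only an increase in WASO.

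This is the named statistic for the primary hypothesis. A programmer or an independent replicator who codes the formula would run a different test from one who codes the next sentence.

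**Working it through.** **Inputs.** Doses 0, 5, 10, 25 and 50 mg (SAP 2). ED50 of 1.11, 3.75 and 15, plus a linear model (SAP 7.3.1.1). From protocol 10.5: maximum effect 25 min, SD 40 min, 50 subjects with 8% unavailable, zero within-subject correlation, two-sided 5%. Hence n = 50 × 0.92 = 46 per dose, and df = 5 × 46 − 5 = 225.

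**Contrasts.** With S = (40²/46)·I, the SAP's optimal contrast is the centred shape scaled to length 1. The standard error of a dose mean is 40/√46 = 5.90 min. The size of the expected T for the matching contrast is the length of the centred mean vector divided by 5.90.

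- True linear, 0.5 min per mg: centred doses are −18, −13, −8, 7, 32, with sum of squares 1630. Expected size = 0.5 × √1630 / 5.90 = 20.19/5.90 = 3.42.
- True Emax with ED50 1.11, scaled to 25 min at 50 mg: means are 0, 20.9, 23.0, 24.5, 25.0, with centred length 21.1. Expected size = 21.1/5.90 = 3.58.
- The Emax 1.11 and linear contrasts correlate 0.604. Each is therefore the weak contrast when the other is true: 0.604 × 3.58 = 2.16 and 0.604 × 3.42 = 2.07.

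On the post-minus-baseline scale, the expected T_m are:

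| True shape | Emax 1.11 | Emax 3.75 | Emax 15 | Linear |
|---|---|---|---|---|
| Emax 1.11 | −3.58 | −3.49 | −3.01 | −2.16 |
| Emax 3.75 | −3.31 | −3.40 | −3.20 | −2.55 |
| Emax 15 | −2.81 | −3.15 | −3.35 | −3.08 |
| Linear | −2.07 | −2.57 | −3.15 | −3.42 |

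**Reproducing the plan.** I simulated the joint multivariate t distribution (400,000 draws). The two-sided 5% critical value for max|T_m| is 2.253. The first power column below matches the protocol's 89–92% with mean 90%. The protocol's other sample sizes also reproduce: average power is about 90% for 71 subjects at 20 min and for 32 subjects at 30 min.

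| True shape | Any candidate, two-sided (maximum absolute value) | Size of the signed maximum against 2.253 | Upper tail of the signed maximum |
|---|---|---|---|
| Emax 1.11 | 92.0% | 45.7% | about 0% |
| Emax 3.75 | 90.2% | 58.6% | about 0% |
| Emax 15 | 89.4% | 63.5% | about 0% |
| Linear | 89.4% | 41.8% | about 0% |
| Mean | 90.3% | 52.4% | about 0% |

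A hand check of the middle column under the linear model: the weakest contrast alone exceeds 2.253 in size with probability about Φ(2.07 − 2.253) = Φ(−0.18) ≈ 43%. The simulated 41.8% is slightly lower because all four contrasts must exceed it.

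**Type I error.** 5.0% for max|T_m| and 2.8% for the size of the signed maximum, so there is no inflation.

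**Sensitivity.** The protocol calls zero correlation conservative. At an assumed correlation of 0.5 (not a document figure), each expected T_m grows by 1/√0.5 = 1.41. Mean power is then 84.9% for the size of the signed maximum, against 99.6% for max|T_m|.

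**The case against.** The strongest answer is that the formula is not the decision rule. The sentence after it, the second-stage text in SAP 7.3.2.2 and protocol 10.3.2.3 all work from an adjusted p-value for each candidate, and the SAP states that this p-value is two-sided. Rejecting when any of these is below 0.05 is the same as using max|T_m|, and it is this rule, not the literal formula, that gives the stated power. SAP 7.3 also assigns the computation to a named package and version, and nothing suggests that either literal reading would be programmed. This stands. A reader might infer that the primary test lacks its stated power or can only detect harm; the documents do not support that.

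The sign is also less settled than SAP 13.5 suggests. Protocol 10.3.2.3 describes the candidate curves as reductions, SAP 7.3.1.1 expresses the assumed effect as a reduction, and SAP 7.3.2.3 treats higher as better. On a reduction scale max(T_m) points towards benefit. This stands in part: it removes the power loss, but it leaves a one-sided statistic beside a two-sided alternative, and it conflicts with the first-stage model and SAP 13.5. The formula as written agrees with the two-sided specification on neither scale.

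A reader might also object that a two-sided rule lets a worsening count as a demonstrated dose response, and might want a one-sided test. Two-sided 5% is specified consistently in protocol 10.3.2.1 and 10.5 and in SAP 7.3.2.1. The placebo-adjusted means are reported with intervals, and the target dose must be 15 minutes better than placebo. A one-sided 2.5% test has practically the same critical value (2.25) and power. Direction is therefore a matter of preference here, not a defect.

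**Conclusion.** The concern holds as an error in the definition of the primary test statistic. The formula in SAP 7.3.2.1 lacks the absolute value that its two-sided test needs, and it contradicts the sentence that follows it.

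If the formula were coded literally on the SAP's stated scale, power would be 42–64% instead of 89–92%, or about 0% in the upper tail. These figures rest on the protocol's design assumptions (25 min, SD 40 min, 46 per dose, zero correlation) and on the post-minus-baseline sign. Under the any-candidate rule nothing is lost: power is 89.4–92.0% and type I error is 5.0%. No error in sample size or type I error follows.

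The point is small but worth correcting, because it concerns the named statistic for the primary hypothesis and because the sign convention differs between SAP sections.

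**What to change.** 1. In SAP 7.3.2.1, write T_max = max_m|T_m| and refer to its two-sided multiplicity-adjusted p-value. This makes the formula agree with the next sentence and with protocol 10.3.2.3.
2. Use one sign convention throughout. Either keep post minus baseline (SAP 13.5 and first stage) and restate the confidence-limit condition in SAP 7.3.2.3 so that lower is better, or state in SAP 7.3 that the MCP-Mod response is reduction in WASO and change the first-stage description to match.

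The cost is one symbol and one or two sentences in a SAP revision before unblinding. SAP 1 allows changes without amendment only for obvious small formatting or spelling errors, and a primary test statistic should not rely on that allowance. No protocol amendment is needed, and sidedness, alpha, sample size and power do not change.

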### 7.3.2.2 Implementation of the Mod step

The Mod step involves model selection, fitting the univariate dose response profile, and estimating target dose(s) based on the fitted model.

A two-stage approach will be used to fit the dose-response model to the observed data. This approach utilizes generalized least squares [Pinheiro 2014] and relies on asymptotic

results, but has the appeal of being a general purpose application as it depends only on  $\hat{\mu}_d$  and  $\hat{S}$ . For example, the obtained (adjusted) estimates for  $\hat{\mu}_d$  and  $\hat{S}$  inherit the missing data assumptions of the underlying first stage model.

#### *First stage*

A linear mixed effects model (first stage model) will be used to calculate estimates for  $\hat{\mu}_d$  (i.e., least squares [LS] mean estimates for each ACT-541468 dose level and placebo) and  $\hat{S}$  (i.e., variance-covariance matrix of  $\hat{\mu}_d$ ).

The change from baseline in WASO (assumed to be normally distributed) will be modeled using a fixed effect for dose group (placebo and each ACT-541468 dose level), an additional fixed effect for period (five periods), a linear slope to adjust for WASO at baseline, and a random effect for subject.

The variance of the change from baseline in WASO is assumed to be constant across each dose group, therefore a compound symmetry structure for  $\hat{S}$  will be considered.

The LS mean for each treatment group will be displayed along with associated standard errors and 95% confidence intervals (CIs). For each ACT-541468 dose level comparison to placebo, the placebo-adjusted LS mean will be displayed along with associated standard error, 95% CI and unadjusted two-sided  $p$ -value.

#### *Second stage*

Among the candidate dose response models with a significant contrast test (i.e., adjusted two-sided  $p$ -value < 0.05) identified in the MCP step, the dose response model parameters (e.g.,  $ED_{50}$ ) are estimated by fitting the dose response model (family) to the estimates obtained from the mixed effects model ( $\hat{\mu}_d$  and  $\hat{S}$ ) in the first stage. The best fitting dose response model ( $E_{\max}$  or linear) will be selected based on the gAIC (smaller is better). This chosen dose response model will then be used to estimate the target dose.

Based on the selected dose response model, the predicted mean (95% CI) dose response profile for the change from baseline in WASO will be graphically displayed.

#### **7.3.2.3 Dose selection based on WASO**

Estimation of a target dose (TD) will be performed on the basis of the fitted dose response model ( $E_{\max}$  or linear) chosen in the second stage. The estimated TD will be the lowest dose strength anywhere within the studied dose range (0 mg to 50 mg) which shows a clinically meaningful effect (i.e., 15 minutes better than predicted mean value of placebo) and a statistically significant effect (i.e., lower 95% CI of the predicted mean value at TD > observed mean value of placebo). Note: the choice of 95% CI is not driven by the purpose of controlling type I error rates.

To aid understanding of the accuracy/variation associated with the selected dose response model, the following parameters of interest will be derived using a nonparametric bootstrap technique.

- The 0.025, 0.5 (median) and 0.975 bootstrap percentiles of the predicted mean (on the change in reduction in WASO of ACT-541468 relative to placebo) for the chosen dose response model,
- The 0.025, 0.5 (median) and 0.975 bootstrap percentiles of the target dose defined as 15 minutes better than predicted mean value of placebo,
- The 0.025, 0.5 (median) and 0.975 bootstrap percentiles of the target dose defined as 20 minutes better than predicted mean value of placebo,
- If the  $E_{\max}$  model is selected, the 0.025, 0.5 and 0.975 bootstrap percentiles of the  $E_0$ ,  $ED_{50}$  and  $E_{\max}$  will be presented.

The nonparametric bootstrap technique will proceed as follows:

1. Sample, with replacement, the data available at each period per subject until the resampled dataset contains the same number of subjects as in the original dataset,
2. From the resampled dataset, calculate and store the parameter estimates that define the dose response model,
3. Repeat steps 1 and 2 numerous times (say 1000) to derive the bootstrap distribution for each parameter,
4. Use the bootstrap distribution to calculate the parameters of interest described above.

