##### **7.3.1.1 Candidate dose response models**

To begin, the set of pre-specified candidate parametric dose response models that could possibly represent the underlying dose response shape are determined. For this study,

four pre-specified dose response models are considered: three  $E_{\max}$  models and one linear model. A graphical display of these models is shown in Figure 2. Here, the maximum mean reduction in WASO from baseline to Days 1 and 2 with ACT-541468 50 mg dose is assumed to be 25 minutes longer than with placebo.

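### SAP 7.3.2.3 judges the target dose by the CI of one predicted mean against the observed placebo mean, not by the protocol's placebo-corrected CI, and does not declare the change

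*SAP*

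**What the plan says.** **Protocol.** Section 10.3.2.3, and the synopsis in the same terms, defines the target dose by a "placebo-corrected mean reduction from baseline in WASO of at least 15 minutes with a 95% confidence interval excluding 0". An interval that excludes 0 can only be an interval for a difference from placebo.

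**SAP.** Section 7.3.2.3 sets two conditions for the lowest qualifying dose between 0 and 50 mg:

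- clinical relevance: "15 minutes better than predicted mean value of placebo";
- statistical significance: "lower 95% CI of the predicted mean value at TD > observed mean value of placebo".

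A note after these conditions says that the 95% level was not chosen to control type I error.

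**Scale.** SAP 7.3.1.1 speaks of the "maximum mean reduction in WASO from baseline to Days 1 and 2 with ACT-541468 50 mg dose", and the first bootstrap item in 7.3.2.3 is "on the change in reduction in WASO of ACT-541468 relative to placebo". The first-stage model, however, is for change from baseline. The second stage says that "the predicted mean (95% CI) dose response profile for the change from baseline in WASO will be graphically displayed", and SAP 13.5 states "A positive number indicates an increase as compared to baseline", so improvement in WASO is negative on that scale.

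**Declared changes.** SAP 12.1 lists only the switch of analysis set for secondary and exploratory efficacy endpoints. SAP 12.3, the place for clarifications of statistical methods, is marked as not applicable.

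**The concern.** The two documents give different criteria for the same output.

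1. **Comparator and interval.** The SAP compares the lower limit of one predicted mean with a placebo estimate taken as a fixed number. The sampling error of placebo is missing. So is the covariance between the two means, although each subject is planned to receive placebo and every dose. The interval therefore has the wrong width for the comparison that it is said to make.
2. **Two placebo references.** One sentence uses predicted placebo for the 15 minutes and observed placebo for the interval, without a reason.
3. **No declaration.** A reader of SAP 12 would not learn that the protocol's criterion had changed.
4. **Scale.** The inequality points the right way for reduction in WASO and the wrong way for change from baseline. The SAP does not say which is meant.

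At stake is the meaning of the significance label on the target dose, which is an output of the modelling step in a study meant to select a dose.

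**Working it through.** **Inputs.** Protocol 10.5: SD 40 min, maximum effect 25 min, 50 subjects with 8% not available (50 × 0.92 = 46), two-sided 5%, within-subject correlation rho = 0. SAP 7.3.1.1: one linear and three Emax shapes with ED50 1.11, 3.75 and 15. Values of rho above 0 are my assumption.

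**Step 1: the plan's own figure.** Simulating the maximum of the four optimal contrasts at n = 46 gives power of 89.5% (linear), 92.1% (ED50 1.11), 90.3% (3.75) and 89.5% (15), average 90.4%. The protocol states 89–92%, average 90%. The inputs reproduce it.

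**Step 2: interval widths for raw means.**

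- One mean: 1.96 × 40/√46 = 11.6 min, whatever rho is.
- Difference from placebo: 1.96 × 40 × √(2(1 − rho)/46).

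| rho | One mean | Difference |
|---|---|---|
| 0 | 11.6 | 16.3 |
| 0.25 | 11.6 | 14.2 |
| 0.5 | 11.6 | 11.6 |
| 0.75 | 11.6 | 8.2 |

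On this scale the SAP width is too narrow below rho = 0.5 and too wide above it.

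**Step 3: fitted-model standard errors.** The SAP rule uses a fitted curve, so these matter more. Delta method, rho = 0, at the dose whose true effect is 15 min; lower limit = 15 − 1.96 × SE:

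| True shape | SE of predicted mean | SE of difference | Lower limit, SAP | Lower limit, protocol |
|---|---|---|---|---|
| Linear | 3.17 | 4.38 | 8.8 | 6.4 |
| ED50 1.11 | 10.87 | 12.04 | −6.3 | −8.6 |
| ED50 3.75 | 4.96 | 7.54 | 5.3 | 0.2 |
| ED50 15 | 3.95 | 7.56 | 7.3 | 0.2 |

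The limits differ, but both fall on the same side of 0 in every row. If the fit equals the true curve, the selected dose differs only for ED50 1.11. For the other shapes the 15-minute condition decides.

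**Step 4: how often the rules disagree.** I simulated 10,000 trials in each of 16 scenarios (four shapes; rho 0, 0.25, 0.5, 0.75), with covariance S = (1600/46)[(1 − rho)I + rho J] treated as known. The steps were the two-sided maximum-contrast gate (critical value 2.238; simulated power at rho 0 of 90–92%), a generalized least squares fit of the families with a significant contrast, choice by gAIC, and a 0.1-mg dose grid. Observed placebo was taken as the first-stage placebo estimate. The scale was reduction.

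| Disagreement | Trials of 160,000 | Largest in any scenario |
|---|---|---|
| Whether a target dose exists | 219 (0.14%) | 0.88% |
| Dose differs by more than 1 mg | 1,397 (0.87%) | 2.67% |
| Either | 1,616 (1.0%) | 3.30% (linear, rho 0.25) |

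In all 219 the SAP rule withholds a dose that the protocol rule grants. Among the 1,397, the SAP dose is higher in 873 (845 with a true linear shape) and lower in 524 (all at rho 0). Choosing by gAIC between both families, whether or not their contrast is significant, gives 218, 1,387 and 1,605. Repeat runs of the same scenarios gave 659 of 64,000 (1.03%) and 241 of 24,000 (1.0%).

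**Step 5: source.** Keeping the single-mean interval but using predicted placebo removes all 219 existence disagreements. It cuts the total from 1,616 to 520 (0.33%), all at rho 0. The reason is the gap between observed and fitted placebo. For a linear fit, the leverage at dose 0 is 1/5 + 18²/1630 = 0.399 (mean dose 18, sum of squares 1,630). The SD of the gap is √(34.78 × 0.601) = 4.6 min at rho 0, and half that, 2.3 min, at rho 0.75. For Emax fits it is at most 1.4 min.

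**Step 6: scale.** On change from baseline, the 15-minute condition puts the predicted mean at least 15 min below predicted placebo. Its lower limit could then exceed observed placebo only if observed placebo lay more than 15 min below predicted placebo, over three SDs (15/4.6 = 3.3). The rule would almost never return a dose, so reduction must be the intended scale.

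**The case against.** The case on the other side has five parts.

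- **The SAP disclaims error control for this interval.** The note is there, but it explains the choice of 95%. It does not explain why the interval is for one mean or why the comparator is observed placebo.
- **The target dose is one input among several.** Protocol 10.5 says that the study is not powered for a given precision of the target dose, and 10.3.2.1 says that dose selection also weighs clinical criteria. Protocol section 10 leaves full details to the SAP. This stands as a reason for low weight. Changing a criterion that the protocol spells out is still more than adding detail.
- **Placebo-relative results are reported anyway.** True. For each tested dose, "the placebo-adjusted LS mean will be displayed along with associated standard error, 95% CI", and bootstrap percentiles relative to placebo are planned. Neither is the selection criterion.
- **The effect is negligible, and the width of the interval is the lesser cause.** Both parts stand. About 1% of simulated trials differ, no trial gained a target dose under the SAP rule that the protocol rule denied, and most of the disagreement comes from observed placebo (step 5). At the planning value rho = 0 no between-subject variance cancels, so that part of the argument rests on an assumed rho. The raw widths in step 2 illustrate the principle and do not measure the rule.
- **The scale is clear from context.** Largely so; this part is editorial.

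**Conclusion.** The point holds as a minor one. The SAP criterion is not the protocol's, mixes two placebo references, leaves its scale unstated and is not declared in SAP 12. The significance label on the target dose would not mean what the protocol says.

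The consequence for the dose is small and has no consistent direction. This rests on the protocol's planning values, compound symmetry, the four candidate shapes, rho from 0 to 0.75 and a 1-mg threshold. With a 0.5-mg threshold the doses differ in up to 19.2% of trials (ED50 1.11, rho 0), but there the true 15-minute dose is 1.6 mg, below the lowest tested dose of 5 mg. The multiple-contrast test, its type I error and its power do not depend on this rule.

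**What to change.** In SAP 7.3.2.3:

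1. State that the inequality is on the scale of reduction in WASO, or reverse it for change from baseline.
2. Replace the bracketed significance condition with: the 95% CI of the model-predicted placebo-corrected effect, f(TD) − f(0), excludes 0 in the direction of benefit.
3. Use predicted placebo in both conditions.
4. Name one source for that interval in advance, either the fitted-model covariance or the planned placebo-relative bootstrap, because the two can give different limits.

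If the sponsor prefers the single-mean rule, list it in SAP 12.1 as a change from Protocol 10.3.2.3, with the reason.

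The cost is a few lines of text. The fitted model, its covariance and the bootstrap are already planned, and no new data or analysis is needed.
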